7.4.2 Persistent or Recurrent Adverse Events

A persistent AE is one that extends continuously, without resolution, between patient evaluation time points. Such events should only be recorded once on the SAE Report Form. If a persistent AE becomes more severe or lessens in severity, AE should be recorded separately with new onset date in eCRF.

A recurrent AE is one that occurs and resolves between patient evaluation time points, and subsequently recurs. All recurrent events should be recorded separately on an SAE Report Form and eCRF and should be reconciled later as a one event. Example of recurrent AEs include, but not limited to recurrent fall, recurrent transaminitis, recurrent elevated GGT.

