8.8.2 Adverse Events

Adverse events (AEs) will be coded using the Medical Dictionary for Regulatory Activities MedDRA Version 24.0 (Hierarchy) for the Safety Analysis Set.

The analyses of safety will be based on the frequency of adverse events and their severity for patients in each portion who received at least one dose of study treatment.

Adverse events will be summarised by system organ class and preferred term; a patient will only be counted once per system organ class and once per preferred term within a treatment according to the maximum NCI CTCAE v.5.0 grade attained. Patient counts and percentages and event counts will be presented for each treatment and overall for all the summaries.

Treatment Emergent Adverse Events (TEAEs) are events with start date on or after the date of first dose of treatment or events with start date prior to the date of first dose of treatment whose severity worsens on or after the date of first dose of treatment.

An overall summary of TEAEs (number and percentage of patients along with the number of events) will be presented with the following:

- Any non-TEAE
- Any TEAE
- Related TEAEs
- Serious TEAEs
- Related Serious TEAEs
- Grade >=3 TEAEs
- Related Grade >=3 TEAEs
- TEAEs leading to discontinuation
- Related TEAEs leading to discontinuation
- TEAEs leading to dose reduction
- Related TEAEs leading to dose reduction
- Serious TEAEs leading to discontinuation
- Related Serious TEAEs leading to discontinuation
- TEAEs leading to dose interruptions
- Related TEAEs leading to dose interruptions
- Fatal TEAEs
- Related Fatal TEAEs
- Protocol-Defined Adverse Events of Special Interest:
 - Pregnancy, abortion, birth defects/congenital anomalies
 - Overdose

Summaries showing the number of patients (n, %) along with number of events by SOC and PT will be provided for the following:

- 1. TEAEs
- 2. Grade 3. 4 and 5 TEAEs
- 3. Treatment-related TEAEs
- 4. TEAE with maximum CTCAE grade
- 5. Treatment-Emergent SAEs
- 6. Treatment-Related SAEs

Document Date: 12MAY2023

- 7. Treatment-related TEAEs with maximum CTCAE grade
- 8. TEAEs leading to dose reduction or interruptions
- 9. Treatment-related TEAEs leading to dose reduction or interruptions

Page 19 of 106 ST-AD-032 version 01

- 10. TEAEs leading to Discontinuation of Study Drug
- 11. Treatment-related TEAEs leading to Discontinuation of Study Drug
- 12. Deaths

No statistical inference between the treatments will be performed on adverse events.

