Percentages are based on the total number of patients (N) in each treatment group.

Treatment-Emergent Adverse Events are those that start on or after the date of first dose of study drug.

Discontinuation refers to discontinuation of study drug.

Patients under the category 'Drug interruption followed by dose reduction' are counted in both the groups 'Drug interruption' and 'Dose reduction'.

^The dose reduction information is collated from the treatment exposure page of the eCRF.

n: Number of patients with any event, E: Number of events, TEAE: Treatment-Emergent Adverse Event.

Reference Listing 16.2.x.x

Document Date: 12MAY2023.

Protocol RP6530-2101

Page xx of yy

Table 14.3.1.2

Treatment-Emergent Adverse Events by System Organ Class and Preferred Term

Safety Analysis Set

System Organ Class Preferred Term		Tenalisib 800 mg (N=xx)	BID	,	Γenalisib 1200 mg (N=xx)	BID		Overall (N=xx)	
	Related n (%), E	Not Related n (%), E	Total n (%), E	Related n (%), E	Not Related n (%), E	Total n (%), E	Related n (%), E	Not Related n (%), E	Total n (%), E
At Least one TEAE	x (xx.x), xx	x (xx.x), xx							
SOC1 PT1 PT2 Etc.	x (xx.x), xx x (xx.x), xx x (xx.x), xx	x (xx.x), xx							

Percentages are based on the total number of patients (N) in each treatment group.

n: Number of patients with any event, E: Number of events, TEAE: Treatment-Emergent Adverse Event

A patient with two or more adverse events in the same system organ class (or with the same preferred term) is counted only once for that system organ class (or preferred term).

Treatment-Emergent Adverse Events are coded using MedDRA (version 24.0)

A patient experiencing an adverse event at multiple occasions with distinct relationships status with study treatment is counted under both "Related" and "Not Related" categories. The events (E) are counted as per their relationship with the study treatment.

System organ classes are sorted in alphabetical order. Preferred terms are sorted within system organ class by descending order of frequency of overall preferred terms.

Treatment-Emergent Adverse Events are those that start on or after the date of first dose of study drug.

Reference Listing 16.2.x.x

Program: xx.sas Table Generation: ddmmmyyyy hh:mm:ss

Use same format for

Table 14.3.1.3 Treatment-Emergent Grade 3, 4 and 5 Adverse Events by System Organ Class and Preferred Term – Safety Analysis Set

Protocol RP6530-2101 Page xx of yy

Table 14.3.1.4

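### AE records are split at every grade change and the SAP never links them, so its event counts can track grade steps and an improving pre-dose AE can be flagged as treatment-emergent

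*Protocol*

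**What the plan says.** **Recording (Protocol 7.4.2).** For an AE that continues without resolving: "If a persistent AE becomes more severe or lessens in severity, AE should be recorded separately with new onset date in eCRF". On the safety form the rule is the opposite: "Such events should only be recorded once on the SAE Report Form". For an AE that resolves and comes back: "All recurrent events should be recorded separately on an SAE Report Form and eCRF and should be reconciled later as a one event". The section does not say who reconciles, in which dataset, or which onset date is kept. Recurrent transaminitis is one of its examples.

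**Counting (SAP 8.8.2).** "Patient counts and percentages and event counts will be presented for each treatment and overall for all the summaries". The table shells gloss E only as the number of events. Patients are counted once per system organ class and preferred term, at maximum CTCAE grade.

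**Treatment emergence.** SAP 8.8.2 has two limbs. The first is "Treatment Emergent Adverse Events (TEAEs) are events with start date on or after the date of first dose of treatment". The second takes an AE that began earlier and worsened on or after first dose. The footnotes to Tables 14.3.1.1, 14.3.1.2, 14.3.1.4 and 14.3.1.6, and the programmer's note for Listings 16.2.7.2 to 16.2.7.8, give the first limb only: "Treatment-Emergent Adverse Events are those that start on or after the date of first dose of study drug".

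No part of the SAP links records of one continuing AE. SAP 7.3 imputes incomplete dates but does not join records.

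**The concern.** The recording rule and the counting rule use different units. The protocol creates a record per grade level; the SAP reads records as events. A toxicity that resolves in steps then adds more to E than the same toxicity recorded at one grade, and E also depends on how often grade is checked. Table 7 of the protocol calls for weekly or twice-weekly monitoring during several toxicities. Listing 16.2.7.1 prints a duration per record, so one long event appears as several short ones.

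The onset date matters as well. A grade decrease after first dose produces a record dated on treatment, and the first TEAE limb looks only at that date.

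The trial compares two doses of 20 patients each, and Protocol 1.5.2 seeks the dose with a signal of efficacy and acceptable safety. AEs are a secondary endpoint and are reported descriptively, so readers will take the printed counts at face value.

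**Working it through.** The documents give no figure to reproduce. The check applies Protocol 7.4.2 and the SAP 8.8.2 definition to five constructed histories (assumptions, not trial data). Day 1 is first dose. The third column counts records whose start date is on or after day 1.

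| History | Clinical episodes (treatment-emergent) | TEAE records as written | With linked events |
|---|---|---|---|
| 1. On treatment, grades 1-2-3-2-1 from days 10, 20, 27, 35, 42, no gap | 1 (1) | 5 | 1 |
| 2. Grade 2 from day -5, eases to grade 1 on day 8 | 1 (0) | 1 | 0 |
| 3. Grade 1 from day -5, worsens to grade 2 on day 8 | 1 (1) | 1 | 1 |
| 4. Three grade 2 episodes from days 10, 40, 70, resolved between | 3 (3) | 3 if separate, 1 if reconciled | 3 |
| 5. Grade 1 from day -5, resolves, recurs at grade 1 on day 20 | 2 (1) | 1 if separate, 0 if reconciled to the first onset (assumed) | 1 |

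**History 1: event count and duration.** E = 5 for one episode; the patient is still counted once, at grade 3. If each record ends the day before the next begins, the first four durations listed are 20 - 10 = 10, 27 - 20 = 7, 35 - 27 = 8 and 42 - 35 = 7 days, followed by a fifth record. No line shows that the event had already run 10 + 7 + 8 + 7 = 32 days. For a laboratory AE, Protocol 7.4.3 records every Grade 3 or 4 value but a Grade 1 or 2 value only if clinically significant. If none of the four lower steps qualifies, E = 5 - 4 = 1. The range is 1 to 5.

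**History 2: false TEAE.** The day 8 record meets the first limb although nothing emerged or worsened. If the patient has no other TEAE under that term, n rises by one, which is 1/20 = 5 percentage points in an arm of 20.

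**Can history 2 occur?** Protocol 7.1.2 collects AEs from consent, and Table 14.3.1.1 has a row for AEs that are not treatment-emergent. Against this, Protocol 6.3.2 sends most events between consent and first dose to Medical History, and 7.4.6 makes a pre-existing condition an AE only if it worsens. The case is possible but uncommon. Protocol 6.3.2 and 7.1.2 also conflict with each other.

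**Rough scale for one term.** Protocol 1.4 gives 7.4% for related Grade 3 or higher ALT increase: 20 x 0.074 = 1.48, about 1.5 patients per arm. If each had one episode stepping 3-2-1 to resolution with every step recorded, expected E = 1.48 x 3 = 4.4 records for about 1.5 events. The rate comes from patients with haematological malignancies at 25 to 1200 mg BID, so it is only an illustration.

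**The case against.** The best defence is that the protocol's own safety measures barely depend on E. Protocol 9.4.2 rests on incidence and worst grade per patient, without inference, and SAP 8.8.2 counts each patient once per term at maximum grade. For AEs starting after first dose, splitting changes neither. This stands and limits the point to E, the event-level listings and durations, plus the pre-dose case.

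Several stronger readings are tempting but are not supported:

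- A reader might infer that recurrences are lost from the tables. Protocol 7.4.2 first records them separately in the eCRF, and the SAP has no merging step. What is missing is a statement of which records E uses.
- A reader might infer that Table 14.3.1.6 shows a recovering Grade 3 event again at Grades 2 and 1. Its footnote takes the highest grade per patient. Whether lower-grade records still enter E there is unclear, no more.
- A reader might apply the 15.6% rate for related ALT increase to a three-step Grade 3 example and claim 9 records for 3 events per arm. That rate covers all grades; the Grade 3 or higher rate is 7.4%.
- A reader might infer that the rule biases the comparison between doses. Both arms record and monitor under the same rules, and nothing says that E decides the dose. A difference would arise only if resolution patterns differ.
- The worsening limb missing from the footnotes does little harm while records are split, because a worsened AE gets a new on-treatment onset anyway (history 3).

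**Conclusion.** The point holds in a limited form. Following the stated rules, E and the listed durations measure grade steps rather than events: 1 to 5 for the single continuous AE in history 1, depending on which steps are recorded. E for three recurrences is undetermined between 3 and 1. Patient n (%) and maximum grade are sound for AEs that begin after first dose. For the small group of AEs recorded before first dose, improvement on treatment can create a false TEAE and move n (%) by one patient.

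This rests on sites following Protocol 7.4.2 as written and on the SAP treating each eCRF record as an event, since it gives no other rule. The actual frequency cannot be derived from the documents. It is worth correcting because the event counts are printed in every AE summary and the correction is small.

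**What to change.** In SAP 8.8.2:

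1. Link consecutive eCRF records of the same preferred term in a patient when there is no resolution between them. The linked event takes the first onset date, the last end date and the maximum grade.
2. Count E, and list durations, on linked events. Count episodes separated by resolution as separate events, from the original eCRF records and not a reconciled version. Confirm that reconciliation has not overwritten those records.
3. Flag a TEAE only if the linked event starts on or after first dose, or if its grade then exceeds the pre-dose grade.
4. Put that definition into the footnotes of the AE tables and the note for Listings 16.2.7.2 to 16.2.7.8. Once records are linked this is essential: history 3 would carry onset day -5, and a start-date-only footnote would drop a true worsening.

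The cost is one derivation and a programming step, using term, dates and grade already collected. Rewording Protocol 7.4.2 would achieve little now, because SAP 5.1 reports that the study closed early.

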7.4.3 Abnormal Laboratory Values

Any grade 3 or 4 laboratory abnormalities and clinically significant grade 1 or 2 laboratory value(s) should be recorded as an AE. Isolated laboratory abnormality without clinical significance should not be captured as AE if confirmed by the investigator. If an abnormal laboratory value or vital sign is associated with clinical signs and/or symptoms, the sign or symptom should be reported as an AE, and the associated laboratory value or vital sign should be considered additional information that must be collected on the relevant eCRF. If the laboratory abnormality is a sign of a disease or syndrome, only the diagnosis needs to be recorded on the SAE Report Form or AE eCRF.

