1.4 Clinical Experience

As of 20th April 2021, a total of 169 patients with relapsed/refractory hematological malignancies (viz. CLL, PTCL, CTCL and iNHL) have been exposed to tenalisib in either single agent or combination studies; 35 patients in RP6530-1301 study, 58 patients in RP6530-1401 study, 2 patients in RP6530+Pembrolizumab-1701 study, and 33 patients RP6530+Romidepsin-1805 study, 20 patients in RP6530-1802 study, 21 patients in RP6530-1901 study. A total of 16 patients have been rolled over to compassionate study (RP6530-1803); 4 from RP6530-1401 study, 5 from RP6530+Romidepsin-1805 study and 7 from RP6530-1901 study. In addition, 18 healthy volunteers were exposed to tenalisib in food effect study (RP6530-1501).

• Safety:

169 patients have received tenalisib at doses ranging from 25-1200 mg BID. Tenalisib is generally well tolerated in patients with hematological malignancies (at doses ranging from 25 mg BID to 1200 mg BID) and aggressive lymphomas such as TCL (at doses ranging from 200 mg BID to 800 mg BID). The most frequently reported related AEs (all grades) that occurred in more than 10% of patients included alanine aminotransferase (ALT) increased, aspartate aminotransferase (AST) increased (15.6% each) and diarrhea (11.9%). The most frequently reported related Grade ≥3 AEs were ALT increased, AST increased (7.4% each) and neutropenia (4.4%). Other Grade ≥3 laboratory abnormalities included gamma-glutamyl transferase (GGT) increased, International normalized ratio (INR)

CONFIDENTIAL Page 19 of 66

increased, hyperglycemia and hypertriglyceridemia reported in one patient each. Hypophosphatemia and thrombocytopenia were reported in two patients.

Pharmacokinetics:

In RP6530-1301 study, pharmacokinetics (PK) was evaluated in patients with hematological malignancies at doses ranging from 25-1200 mg BID and in TCL at doses ranging from 200 to 800 mg BID. Maximum systemic exposures assessed by AUC_{0-t} as determined on Cycle 1 Day 1 (C1D1) were found at these doses. Tenalisib showed rapid absorption (between 0.5 and 2 h), with C_{max} and AUC_{0-t} increasing proportionately with dose on C1D1. There was no significant accumulation between C1D1 and C2D1. Trough concentrations did not show any specific trends from one day to the other even though concentrations increased generally with doses. $T_{1/2}$ were similar for all dose levels.

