3.1.2 Secondary Endpoints

- Overall Response Rate (ORR), Clinical Benefit Rate (CBR) and Progression Free Survival (PFS).
- Adverse event (AE), Grade 3/4 AEs, serious adverse event (SAE) evaluated and graded using NCI-CTCAE Version 5.0.

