7 ASSESSMENT OF SAFETY

7.1 Adverse Events

7.1.1 Definitions of Adverse Events

Any untoward medical occurrence in a patient or clinical investigation subject administered a pharmaceutical product and which does not necessarily have a causal relationship with this treatment. An adverse event (AE) can therefore be any unfavorable and unintended sign (including an abnormal laboratory finding), symptom, or disease temporally associated with the use of an investigational product, whether or not related to the investigational product.

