9.2 Determination of Sample Size

A sample size of 20 per group will provide a precision of 13% for a two-sided 90% confidence interval based on Exact (Clopper-Pearson) method assuming the percentage of patients without progression at the end of 6 month is 20%. Thus, total 40 patients (20 patients in each group) will be enrolled in the study.

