^{*:} Non-treatment-emergent adverse events

Use same format for

Document Date: 12MAY2023.

<Note to Programmer: Please add the footnote "Treatment-Emergent Adverse Events are those that start on or after the date of first dose of study drug.">

Listing 16.2.7.2 Treatment-Related TEAEs - Safety Analysis Set

Listing 16.2.7.3 Treatment-Emergent Grade 3, 4 and 5 Adverse Events - Safety Analysis Set

Listing 16.2.7.4 Treatment-Related Grade 3, 4 and 5 TEAEs - Safety Analysis Set

Listing 16.2.7.5 Treatment-Emergent Serious Adverse Events - Safety Analysis Set

Listing 16.2.7.6 Treatment-Related Serious TEAEs - Safety Analysis Set

Listing 16.2.7.7 Treatment-Emergent Adverse Events leading to Discontinuation of study drug - Safety Analysis Set

Listing 16.2.7.8 Treatment-Emergent Adverse Events leading to death - Safety Analysis Set

Page 86 of 106

ST-AD-032 version 01

Protocol RP6530-2101 Listing 16.2.8.1.1 Clinical Laboratory Evaluations – Hematology Safety Analysis Set Page xx of yy

Patient ID	Treatment Group	Visit	Date/Time of Collection	Test Name	Result	Unit	LLN	ULN	Normal/Abnormal	In case of CS, Specify AE No
Xxxx	Xxxxxx	Screening	DDMMMYYYY/ hh:mm	Xxxx	XX.X	XX	XX.X	XX.X	Normal	5
				Xxxx	xx.x	XX	XX	XX	Abnormal, NCS	

NCS: Not Clinically Significant; CS: Clinically Significant; EOT: End of Treatment; Clinical significance is applicable if results are out of reference range; LLN: Lower Limit of Normal; ULN: Upper Limit of Normal

Program: xx.sas Listing Generation: ddmmmyyyy hh:mm:ss

Use same format for

Document Date: 12MAY2023.

Listing 16.2.8.2.1 Clinical Laboratory Evaluations - Biochemistry - Safety Analysis Set

Page 87 of 106 ST-AD-032 version 01

Protocol RP6530-2101 Listing 16.2.8.1.2 Abnormal Laboratory Values – Hematology Safety Analysis Set Page xx of yy

Patient Treatment ID Group	Visit	Date/Time of Collection	Test Name	Result	Unit	LLN	ULN	Clinically Significant?	In case of CS, Specify AE No
Xxxx Xxxxx	Screening	DDMMMYYYY/hh:mm	Xxxx	XX.X	XX	XX.X	XX.X	No	_
			Xxxx	XX.X	XX	XX.X	XX.X	No	
			Xxxx	XX.X	XX	XX.X	XX.X	No	
			Xxxx	XX.X	XX	XX.X	XX.X	No	
	Cycle 1 Day	1 DDMMMYYYY/hh:mm	Xxxx	XX.X	XX	XX.X	XX.X	No	
			Xxxx	XX.X	XX	XX.X	XX.X	No	
			Xxxx	XX.X	XX	XX.X	XX.X	Yes	
			Xxxx	XX.X	XX	XX.X	XX.X	No	

CS: Clinically Significant; EOT: End of Treatment; Clinical significance is applicable if results are out of reference range; LLN: Lower Limit of Normal; ULN: Upper Limit of Normal; AE: Adverse Event.

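### Protocol 7.4.3 gives two opposite recording rules for an isolated Grade 3/4 laboratory value, so some Grade 3/4 events can leave the AE endpoint on the investigator's opinion

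*Protocol*

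**What the plan says.** Protocol 7.4.3 (Abnormal Laboratory Values) opens with "Any grade 3 or 4 laboratory abnormalities and clinically significant grade 1 or 2 laboratory value(s) should be recorded as an AE". Clinical significance is a condition here for Grades 1 and 2 only. The next sentence reads "Isolated laboratory abnormality without clinical significance should not be captured as AE if confirmed by the investigator" and mentions no grade. Values accompanied by signs or symptoms are dealt with separately in the same section, so the exclusion concerns laboratory findings that stand alone.

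The general AE definition in Protocol 7.1.1 covers any "unfavorable and unintended sign (including an abnormal laboratory finding"). Protocol 3.1.2 names as secondary endpoints "Adverse event (AE), Grade 3/4 AEs, serious adverse event (SAE) evaluated and graded using NCI-CTCAE Version 5.0".

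The SAP builds its Grade ≥3 summaries from recorded AEs (SAP 8.8.2). For laboratory data, SAP 8.8.3 and the output list in SAP 12 plan descriptive statistics and listings. Protocol 9.4.2 also plans a tabulation of each patient's worst CTCAE grade for selected laboratory measurements. No such table appears in the SAP, and SAP 5.2 declares no change from the protocol's analyses.

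**The concern.** An isolated Grade 3 or 4 value judged not clinically significant meets both sentences. The first requires an AE record and the second forbids one. Two sites could each follow the protocol and record the same value differently.

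At stake is the comparability of a secondary safety endpoint in a trial that sets out to choose between two doses partly on their safety profile (Protocol 1.5.2). Treatment is open label, so the investigator who judges clinical significance knows the dose. The kind of event affected is also relevant to this drug: Protocol 1.4 reports that its most frequent related Grade ≥3 AEs were ALT and AST increases (7.4% each) and neutropenia (4.4%).

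**Working it through.** No design figure in the plan depends on this point, so there is none to reproduce. The check is a comparison of texts, followed by a rough sizing.

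**1. The two sentences applied to an isolated abnormality**

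| Value | First sentence of 7.4.3 | Second sentence of 7.4.3 |
|---|---|---|
| Grade 1-2, clinically significant | AE | does not apply |
| Grade 1-2, not clinically significant | not listed as an AE | not an AE |
| Grade 3-4, clinically significant | AE | does not apply |
| Grade 3-4, not clinically significant | **AE** | **not an AE** |

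Only the last row conflicts. If the second sentence is confined to Grade 1-2, it mostly restates what the first already implies. It changes a result only for Grade 3-4, so a site could reasonably take it as an exemption.

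**2. Which events could plausibly fall in the last row**

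- Grade 3 neutropenia: Table 6 maintains the dose and asks for ANC at least weekly. With no action on study drug, a judgement of not clinically significant is plausible.
- Grade 3 ALT/AST: Table 7 withholds tenalisib, so the same judgement is harder to defend. Tables 6 and 7 are nevertheless described in Protocol 7.6 as guidance, subject to the investigator's clinical judgement.

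**3. Size**

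Inputs: n = 20 per arm (Protocol 9.2); rates from Protocol 1.4. The share f of Grade ≥3 values left unrecorded is not given in the documents, so it is varied as an assumption.

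Effect of one unrecorded patient who has no other Grade 3/4 AE: 1/20 = 5 percentage points (for example, 2/20 = 10% becomes 1/20 = 5%).

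Expected recorded patients per arm = 20 × p × (1 − f). Chance that an arm shows none = (1 − p(1 − f))^20.

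| f (assumed) | Neutropenia, p = 4.4%: expected | none | ALT increase, p = 7.4%: expected | none |
|---|---|---|---|---|
| 0 | 0.88 | 40.7% | 1.48 | 21.5% |
| 25% | 0.66 | 51.1% | 1.11 | 31.9% |
| 50% | 0.44 | 64.1% | 0.74 | 47.0% |
| 75% | 0.22 | 80.2% | 0.37 | 68.8% |
| 100% | 0 | 100% | 0 | 100% |

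Two cautions apply. The 4.4% includes Grade 4 neutropenia, for which Table 6 holds the dose, so it overstates the related Grade 3 part. The rates come from haematological patients across 25-1200 mg BID, in single-agent and combination studies, and their denominator is not stated: of the 169 exposed patients, 12/169 = 7.1% and 13/169 = 7.7%, so 7.4% cannot be a share of 169. Using 12/169 or 13/169 instead gives 1.42 or 1.54 expected ALT cases per arm, which leaves the sizing essentially unchanged.

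**4. Whether the SAP closes the gap**

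It does not. The Grade ≥3 AE tables take the recorded AEs as they are, and the planned laboratory outputs contain no table by CTCAE grade that would reveal a Grade ≥3 value without an AE.

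**The case against.** The strongest reply is that the two sentences can be read together. The first sets out what is recorded, and the second covers what remains: Grade 1-2 values without clinical significance, taken out of the broad definition in 7.1.1. This may well be what was meant. But the text does not say so, and the other reading follows the words as written.

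A reader might infer that the endpoint will lose the drug's main toxicity, asymptomatic ALT/AST rises. The documents do not support that. Table 7 prescribes action from Grade 1-2 transaminitis upward, Protocol 7.4.2 gives recurrent transaminitis as an example of a recurrent AE, and Protocol 4.3 requires follow-up of drug-related Grade ≥3 laboratory abnormalities. These are among the values least likely to be called insignificant. How many past rises were asymptomatic is not reported.

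A reader might also take the laboratory listing shells in SAP 12 as proof that a value marked not clinically significant gets no AE. They ask for an AE number only for clinically significant values, with the footnote "Clinical significance is applicable if results are out of reference range". These are mock layouts and do not govern what sites record; one sample row shows an AE number beside a normal result.

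Nor does it follow that dose holds will be missing from the interruption and reduction tables. Listing 16.2.5.1 records the action on study drug and its reason, with an AE number in the sample row. A hold for toxicity without an AE record should therefore show up.

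Finally, the values themselves are not lost. Results are listed with lower and upper limits of normal, so grades can be rebuilt. This objection stands: the loss is from the AE endpoint and its tables, not from the database.

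**Conclusion.** The conflict is real but narrow. It concerns isolated Grade 3/4 laboratory values judged not clinically significant, most plausibly Grade 3 neutropenia. It makes the Grade 3/4 AE endpoint partly dependent on unblinded opinion that may vary by site or arm.

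The firm part of the size is 5 percentage points per unrecorded patient in an arm of 20, provided she has no other Grade 3/4 AE. How many patients would be affected cannot be stated, because the documents give no share. A reader might go further and infer that one or two such calls would reverse the apparent safety order of the two doses. That would need a share and a between-arm imbalance that the documents do not provide, and both documents rule out formal inference on AEs.

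**What to change.** Reconcile the two sentences of Protocol 7.4.3 by limiting the exclusion to Grade 1-2, in line with the first sentence. For example: an isolated Grade 1 or 2 laboratory abnormality without clinical significance is not recorded as an AE; every Grade 3 or 4 abnormality is recorded, or captured under its diagnosis, whatever its clinical significance.

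SAP 5.1 reports that the study closed early, so a protocol change may come too late to alter collection. At minimum, before database lock:

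- grade the laboratory results by CTCAE v5.0, reconcile Grade ≥3 values against the AE page, and query any without a matching AE or diagnosis;
- add to the SAP the worst-CTCAE-grade laboratory table planned in Protocol 9.4.2, by dose group, or list its omission as a change in SAP 5.2.

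The cost is one sentence, one reconciliation listing and one table. Reported Grade 3/4 AE counts may rise slightly. No dosing or other clinical rule changes.
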